7.6.2. Grades 3 Laboratory Abnormality or Clinical Event

- For Grade 3 clinically significant laboratory abnormality or clinical event, investigational medicinal product may be continued if the event is considered to be unrelated to investigational medicinal product.
- For a Grade 3 clinical event, or clinically significant laboratory abnormality confirmed by repeat testing, that is considered to be related to investigational medicinal product, investigational medicinal product should be withheld until the toxicity returns to \leq Grade 2.
- If a laboratory abnormality recurs to \geq Grade 3 following re-challenge with investigational medicinal product and is considered related to investigational medicinal product, then investigational medicinal product should be permanently discontinued and the subject managed according to local practice. Recurrence of laboratory abnormalities considered unrelated to investigational medicinal product may not require permanent discontinuation.

7.6.3. Grade 4 Laboratory Abnormality or Clinical Event

- For a Grade 4 clinical event or clinically significant Grade 4 laboratory abnormality confirmed by repeat testing that is considered related to investigational medicinal product, investigational medicinal product should be permanently discontinued and the subject managed according to local practice. The subject should be followed as clinically indicated until the laboratory abnormality returns to Baseline or is otherwise explained, whichever occurs first. A clinically significant Grade 4 laboratory abnormality that is not confirmed by repeat testing should be managed according to the algorithm for the new toxicity grade.

Investigational medicinal product may be continued without dose interruption for a clinically non-significant Grade 4 laboratory abnormality (eg, Grade 4 CK after strenuous exercise or triglyceride elevation that is non-fasting or that can be medically managed) or a clinical event considered unrelated to investigational medicinal product.

7.7. Special Situations Reports

7.7.1. Definitions of Special Situations

Special situation reports include all reports of medication error, abuse, misuse, overdose, reports of adverse events associated with product complaints, occupational exposure with an AE and pregnancy reports regardless of an associated AE.

Medication error is any unintentional error in the prescribing, dispensing, or administration of a medicinal product while in the control of the health care provider, subject, or consumer.

Abuse is defined as persistent or sporadic intentional excessive use of a medicinal product by a subject.

Misuse is defined as any intentional and inappropriate use of a medicinal product that is not in accordance with the protocol instructions or the local prescribing information.

An overdose is defined as an accidental or intentional administration of a quantity of a medicinal product given per administration or cumulatively which is above the maximum recommended dose as per protocol or in the product labelling (as it applies to the daily dose of the subject in question). In cases of a discrepancy in drug accountability, overdose will be established only when it is clear that the subject has taken the excess dose(s). Overdose cannot be established when the subject cannot account for the discrepancy except in cases in which the investigator has reason to suspect that the subject has taken the additional dose(s).

An occupational exposure with an AE is defined as an exposure to a medicinal product as a result of one's professional or non-professional occupation.

Product complaint is defined as complaints arising from potential deviations in the manufacture, packaging, or distribution of the medicinal product.

7.7.2. Instructions for Reporting Special Situations

7.7.2.1. Instructions for Reporting Pregnancies

The investigator should report pregnancies in female study subjects that are identified after initiation of study medication and throughout the study, including the post study drug follow-up period to Gilead DSPH using the pregnancy report form within 24 hours of becoming aware of the pregnancy.

Refer to Section [7.3](#) and the CRF/eCRF completion guidelines for full instructions on the mechanism of pregnancy reporting.

The pregnancy itself is not considered an AE nor is an induced elective abortion to terminate a pregnancy without medical reasons.

Any premature termination of pregnancy (eg, a spontaneous abortion, an induced therapeutic abortion due to complications or other medical reasons) must be reported within 24 hours as an SAE. The underlying medical reason for this procedure should be recorded as the AE term.

A spontaneous abortion is always considered to be an SAE and will be reported as described in Sections [7.1.1](#) and [7.1.2](#). Furthermore, any SAE occurring as an adverse pregnancy outcome post study must be reported to Gilead DSPH

The subject should receive appropriate monitoring and care until the conclusion of the pregnancy. The outcome should be reported to Gilead DSPH using the pregnancy outcome report form. If the end of the pregnancy occurs after the study has been completed, the outcome should be reported directly to Gilead DSPH. Gilead DSPH contact information is as follows:
Email: [contact] and [contact].

Pregnancies of female partners of male study subjects exposed to Gilead or other study drugs should also be reported and relevant information should be submitted to Gilead DSPH using the pregnancy and pregnancy outcome forms within 24 hours. Monitoring of the pregnant partner should continue until the conclusion of the pregnancy. If the end of the pregnancy occurs after the study has been completed, the outcome should be reported directly to Gilead DSPH, [contact] or email [contact].

Refer to [Appendix 5](#) for Pregnancy Precautions, Definition for Female of Childbearing Potential, and Contraceptive Requirements.

7.7.2.2. Reporting Other Special Situations

All other special situation reports must be reported on the special situations report form and forwarded to Gilead DSPH within 24 hours of the investigator becoming aware of the situation. These reports must consist of situations that involve study IMP and/or Gilead concomitant medications, but do not apply to non-Gilead concomitant medications.

Special situations involving non-Gilead concomitant medications does not need to be reported on the special situations report form; however, for special situations that result in AEs due to a non-Gilead concomitant medication, the AE should be reported on the AE form.

Any inappropriate use of concomitant medications prohibited by this protocol should not be reported as “misuse,” but may be more appropriately documented as a protocol deviation.

Refer to Section [7.3](#) and the CRF/eCRF completion guidelines for full instructions on the mechanism of special situations reporting.

All clinical sequelae in relation to these special situation reports will be reported as AEs or SAEs at the same time using the AE CRF/eCRF and/or the SAE report form. Details of the symptoms and signs, clinical management, and outcome will be reported, when available.

8. STATISTICAL CONSIDERATIONS

8.1. Analysis Objectives and Endpoints

8.1.1. Analysis Objectives

The primary objective of the study is to assess the efficacy of GS-5745 versus placebo as an add-on therapy to a TNF inhibitor and methotrexate in subjects with moderately to severely active rheumatoid arthritis (RA)

The secondary objectives of this study are as follows:

- To assess the safety and tolerability of GS-5745 versus placebo as an add-on therapy with a TNF inhibitor and methotrexate in subjects with moderately to severely active RA
- To assess the pharmacokinetics (PK) of GS-5745 as an add-on therapy with a TNF inhibitor and methotrexate in subjects with moderately to severely active RA

The exploratory objectives of the study are as follows:

PPD

8.1.2. Primary Endpoint

The primary endpoint is change from Baseline in DAS28(CRP) at Week 12.

[figure not shown]
8.1.3. Secondary Endpoints

Secondary endpoints are:

- Proportion of subjects that achieve DAS28(CRP) ≤ 3.2 at Week 12
- Proportion of subjects that achieve DAS28(CRP) < 2.6 at Week 12
- Plasma concentrations of GS-5745

8.1.4. Exploratory Endpoints

PPD

PPD

8.2. Analysis Conventions

8.2.1. Analysis Sets

8.2.1.1. Full Analysis Set (FAS)

The primary analysis set for efficacy analyses will be the FAS, which includes all randomized subjects who received at least one dose of study drug.

8.2.1.2. Safety Analysis Set

The primary analysis set for safety analyses will be the Safety Analysis Set which includes all subjects who received at least one dose of study drug

8.2.1.3. Pharmacokinetic (PK) Analysis Set

The PK analysis sets includes all subjects in the safety Analysis Set who have the necessary Day 1 and on-study measurements to provide interpretable results for the specific parameters of interest.

8.3. Data Handling Conventions

PK concentration values and PK parameter values below the limit of quantitation (BLQ) will be presented as “BLQ” in the data listings. BLQ values that occur prior to the first dose will be treated as 0, BLQ values at all other time points will be treated as 1/2 of the lower limit of quantitation (LLOQ).

Laboratory data that are continuous in nature but are less than the lower limit of quantitation or above the upper limit of quantitation will be imputed to the value of the lower or upper limit minus or plus one significant digit, respectively (eg, if the result of a continuous laboratory test is < 20, a value of 19 will be assigned; if the result of a continuous laboratory test is < 20.0, a value of 19.9 will be assigned).

8.4. Demographic Data and Baseline Characteristics

Demographic and Baseline measurements will be summarized using standard descriptive methods by treatment group and overall.

Baseline characteristics may include prior use of bDMARD, DAS28(CRP), HAQ-DI, SDAI, CDAI, and other variables of interest.

8.5. Efficacy Analysis

The primary endpoint for the study is change from Baseline in DAS28(CRP) at Week 12, which will be analyzed using a mixed model repeated measures (MMRM) approach that includes the fixed effects of treatment, visit, treatment by visit interaction, and Baseline value, and subject as a random effect.

Secondary endpoints include proportion of subjects that achieve DAS28(CRP) ≤ 3.2 and proportion of subjects that achieve DAS28(CRP) < 2.6 at Week 12. The response rates between each of the two GS-5745 treated groups and the placebo group will be compared using a stratified Cochran-Mantel-Haenszel (CMH) Chi-square test adjusting for stratification factors in randomization. The difference in response rates between treatment groups and the corresponding 95% confidence intervals will be presented.

Sensitivity analyses may be performed for the efficacy assessment.

Details on efficacy analyses will be described in the statistical analysis plan.

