5. INVESTIGATIONAL MEDICINAL PRODUCTS

5.1. Randomization, Blinding and Treatment Codes

Subjects will be assigned a screening number at the time of consent. The Day 1 visit and randomization cannot occur until the investigator has received the results of the screening tests and subject eligibility has been confirmed. Once eligibility is confirmed, each subject will be assigned a unique subject number, which will not be reassigned to any other subject.

At the Day 1 visit, subjects will be randomized in a 1:1:1 ratio to Dosing Group 1, 2, or 3. Randomization will be stratified by disease activity at Screening: DAS28(CRP) > 5.1 or DAS28(CRP) > 3.2 and \leq 5.1. In addition, subjects will be stratified by prior use of RA biologics including the TNF inhibitor being administered during Screening (\geq 3 or $<$ 3). The IXRS will assign blinded study drug numbers at each study drug administration visit, and study drug will be dispensed to the subject in a blinded fashion until Week 12.

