8.9. Sample Size

A total sample size of 75 subjects will be required for this study. Each of the 2 GS-5745 treated groups will be compared to the placebo group. A sample size of 25 per group will provide a power of 80% with a two-sided α level of 0.05 to detect a Minimal Clinically Important Improvement (MCII) in DAS28(CRP) change from Baseline of 1.2 at Week 12 between a GS-5745 treated group and the placebo group, assuming a common standard deviation of 1.35 and 15% early dropout rate.

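### The primary MMRM in Protocol 8.5 omits the prior-biologics stratum that randomisation uses and the secondary test adjusts for; if that factor is prognostic, the primary test is mildly conservative

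*Protocol*

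**What the plan says.** Protocol 5.1 sets two stratification factors. The first is DAS28(CRP), above 5.1 or between 3.2 and 5.1: "Randomization will be stratified by disease activity at Screening". The second is the number of RA biologics, >=3 or <3: "subjects will be stratified by prior use of RA biologics including the TNF inhibitor being administered during Screening".

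Protocol 8.5 then specifies the primary MMRM, which "includes the fixed effects of treatment, visit, treatment by visit interaction, and Baseline value", with a random effect for subject. The next paragraph compares the secondary response rates with a "stratified Cochran-Mantel-Haenszel (CMH) Chi-square test adjusting for stratification factors in randomization". The Synopsis repeats the stratified CMH test and names the MMRM without listing its terms.

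Protocol 8.5 leaves details of the efficacy analyses to the SAP. The SAP was written after the sponsor stopped the study. It tests no hypotheses (6.2.2), summarises the primary endpoint descriptively (6.2.3) and uses no stratification factors or covariates (3.3). The strata appear only as baseline characteristics (5.2).

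**The concern.** The continuous Baseline value largely covers the DAS28(CRP) stratum. Nothing in the model stands in for the biologics stratum.

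Stratified randomisation balances that factor across arms, so whatever outcome variance it explains drops out of the true sampling variance of the treatment difference. A model without the factor still counts that variance as residual error. The standard error is then too large, the confidence interval too wide and the test conservative. This happens only to the extent that the factor is related to outcome after Baseline is accounted for.

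The same section also adjusts the secondary endpoints for the factor and leaves the primary endpoint unadjusted, with no explanation. At stake is a modest amount of precision in a small trial, together with the consistency of the two analyses.

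**Working it through.** **Inputs from Protocol 8.9.** "A sample size of 25 per group will provide a power of 80% with a two-sided α level of 0.05"; the difference is a "DAS28(CRP) change from Baseline of 1.2 at Week 12 between a GS-5745 treated group and the placebo group"; the SD is 1.35 and dropout 15%.

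**The plan's own figure.** With 21 completers per arm the noncentrality of a two-sample t-test is 1.2 / (1.35 × sqrt(2/21)) = 1.2 / 0.4166 = 2.88. On 40 df that gives 80.25% power, and 21 / 0.85 = 24.7, rounded up to 25. The stated sample size reproduces, and it takes no credit for any covariate.

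**Assumptions not in the documents.** About 40% of subjects are in the >=3 stratum, and the mean change differs between strata by d = 0, 0.5, 0.8 or 1.0 units after Baseline. The top of that range is close to the 1.2-unit treatment effect, so it is a generous upper case.

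**Formulas.**
- Residual SD once the stratum is fitted: s = sqrt(1.35² − 0.4 × 0.6 × d²) = sqrt(1.8225 − 0.24 d²).
- Share of variance explained: 0.24 d² / 1.8225.
- True alpha of the unadjusted test under balanced strata: 2 × (1 − Φ(1.96 × 1.35 / s)).

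| d | s | Variance explained | 1.96 × 1.35 / s | True alpha, unadjusted |
|---|---|---|---|---|
| 0 | 1.350 | 0% | 1.960 | 5.0% |
| 0.5 | 1.328 | 3.3% | 1.993 | 4.6% |
| 0.8 | 1.292 | 8.4% | 2.048 | 4.1% |
| 1.0 | 1.258 | 13.2% | 2.103 | 3.5% |

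**Power.** Balance lowers the true variance of the estimate whether or not the model contains the factor, so the power of the unadjusted test also moves with d and must be recomputed. A simulation used two arms of 21, 8 of the 21 in the >=3 stratum in each arm, a difference of 1.2 and 400,000 trials per row.

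| d | Unadjusted | Adjusted | Gain (points) |
|---|---|---|---|
| 0.5 | 80.67% | 81.55% | 0.9 |
| 0.8 | 81.28% | 83.63% | 2.4 |
| 1.0 | 81.82% | 85.46% | 3.6 |

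At d = 0 the noncentral-t calculation gives 80.25% without the factor and 80.2% with it, one df having been spent.

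**Cross-check with three arms.** A second simulation had 75 subjects, stratified blocks of 6, 15% dropout, 30% in the >=3 stratum and 8,000 trials per scenario. With 0%, 5% and 10% of variance explained, power without and with the factor was 81.1% and 81.0%, 81.3% and 82.6%, and 81.5% and 84.5%. Alpha without the factor was 5.1%, 4.7% and 3.9%. With it, alpha stayed between 4.9% and 5.2%.

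Both simulations use a single Week 12 comparison in place of the full MMRM, and neither models the Baseline covariate.

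**The case against.** The strongest reply is that the omission does no demonstrable harm. The stated power assumes an SD of 1.35 with no covariate, so 80% is reached without the factor. Leaving out a balanced factor does not bias the comparison and cannot inflate alpha. All of this stands.

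Three stronger readings are tempting, and the documents support none of them.

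- A reader might infer that the primary test *is* conservative and *does* lose power. That requires biologic count to be prognostic beyond Baseline DAS28(CRP), and no figure for this is given. Protocol 1.3.1 says that responses to single biologics tend to be lower in TNF-inadequate responders than in TNF-naïve subjects. This makes prognostic value plausible, but it is not about a count of three or more.
- A reader might set the adjusted powers of 81.5%, 83.6% and 85.5% against a fixed 80.3% and report gains of 1.2, 3.3 and 5.2 points. That lets stratification lower the alpha of the unadjusted test while ignoring that it also raises its power.
- A reader might think that trial results are affected. The study stopped after 15 subjects (SAP 1.3), and neither the MMRM nor the CMH test is run in the final analysis.

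The deferral of detail to the SAP is a weaker reply. Protocol 8.5 already gives an explicit list of terms, the SAP never adds the factor, and the sensitivity analyses that 8.5 permits are optional and unspecified.

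**Conclusion.** The inconsistency is real: one section adjusts the secondary endpoints for the biologics stratum and leaves it out of the primary model. Its cost is conditional and small. Under the assumed 40% share and differences of 0.5 to 1.0 units, alpha is 4.6% to 3.5% and the power forgone is about 0.9 to 3.6 points; with no prognostic effect nothing is lost. This is an improvement to consider in the protocol's stated primary analysis, or when the design is reused. It is not a defect in any reported result.

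**What to change.** In Protocol 8.5, add the number of RA biologics (<3 or >=3, as used at randomisation) to the MMRM as a fixed effect and keep continuous Baseline DAS28(CRP). Carry the same wording into the Synopsis, or state why the factor is left out. The dichotomised Screening DAS28(CRP) stratum is optional, because the continuous Baseline value largely covers it.

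The cost is one phrase and one degree of freedom: 80.25% power becomes 80.2% if the factor turns out not to matter. The descriptive SAP needs no change.

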8.6. Safety Analysis

All safety analyses will be performed using the safety analysis set.

Safety will be evaluated by assessment of clinical laboratory tests, physical examinations, vital signs measurements at various time points during the study, and by the documentation of AEs.

All safety data collected on or after the first dose of study drug administration up to 30 days after the last dose of study drug will be summarized by treatment group according to the study drug received.

8.6.1. Extent of Exposure

A subject's extent of exposure to study drug will be generated from the study drug administration data. Exposure data will be summarized by treatment group.

8.6.2. Adverse Events

Clinical and laboratory adverse events will be coded using the Medical Dictionary for Regulatory Activities (MedDRA). System Organ Class (SOC), High-Level Group Term (HLGT), High-Level Term (HLT), Preferred Term (PT), and Lower-Level Term (LLT) will be attached to the clinical database. Treatment-Emergent Adverse Events (TEAEs) are:

- Any AEs with an onset date of on or after the study drug start date and no later than 30 days after permanent discontinuation of study drug or
- Any AEs leading to premature discontinuation of study drug.

Summaries (number and percentage of subjects) of TEAEs by SOC and PT will be provided by treatment group. TEAEs will also be summarized by relationship to study drug and severity. In addition, TEAEs leading to premature discontinuation of study drug will be summarized and listed.

8.6.3. Laboratory Evaluations

Selected laboratory data will be summarized (n, mean, SD, median, Q1, Q3, minimum, and maximum) by treatment group and study visit along with corresponding change from Baseline. The incidence of treatment-emergent graded laboratory abnormalities will be summarized similarly. Graded laboratory abnormalities will be defined using CTCAE 4.03 grading scale

8.7. Pharmacokinetic Analysis

The plasma concentration data of GS-5745 will be summarized by nominal sampling time using descriptive statistics (eg, sample size, arithmetic mean, geometric mean, coefficient of variation (%) standard deviation, median, minimum, and maximum). PK parameters (C_{\max} , T_{\max} , C_{last} , T_{last} , AUC_{last} , as applicable) for optional PK sub-study may be listed and summarized using descriptive statistics.

Exposure-response analysis may be explored as appropriate.

8.8. Immunogenicity Analysis

Immunogenicity of GS-5745 will be evaluated based upon the incidence of anti-drug (GS-5745) antibody (ADA) formation. The number and percentage of subjects exhibiting positive ADA results at each specified time point will be summarized. ADA results with supporting data will be included in a listing as well. Impact of ADA on GS-5745 PK, safety, and efficacy may be evaluated as applicable.

8.9. Sample Size

A total sample size of 75 subjects will be required for this study. Each of the 2 GS-5745 treated groups will be compared to the placebo group. A sample size of 25 per group will provide a power of 80% with a two-sided α level of 0.05 to detect a Minimal Clinically Important Improvement (MCII) in DAS28(CRP) change from Baseline of 1.2 at Week 12 between a GS-5745 treated group and the placebo group, assuming a common standard deviation of 1.35 and 15% early dropout rate.

8.10. Data Monitoring Committee

An external multidisciplinary data monitoring committee (DMC) will review the progress of the study and perform interim unblinded reviews of safety data at designated scheduled intervals and provide recommendation to Gilead whether the nature, frequency, and severity of adverse effects associated with study treatment warrant the early termination of the study in the best interests of the participants, whether the study should continue as planned, or the study should continue with

modifications. The DMC may also provide recommendations as needed regarding study design. The DMC's specific activities will be defined by a mutually agreed charter, which will define the DMC's membership, conduct and meeting schedule.

While the DMC will be asked to advise Gilead regarding future conduct of the study, including possible early study termination, Gilead retains final decision-making authority on all aspects of the study.

